4.6 Analysis Populations

All analyses of primary and secondary outcomes, including safety outcomes, will be based on intention-to-treat. Participants would be analysed in the intervention group to which were randomised, and all participants shall be included whether or not they received the allocated intervention.

As a sensitivity analysis, a per-protocol analysis would also be carried out for the primary outcome and secondary outcomes.

5. Definition and Derived variables

5.1 Primary outcome

The primary outcome is the incidence of an episode of delirium during the first 7 postoperative days, assessed daily by the Confusion Assessment Method. An episode is defined if both acute onset and fluctuating course and inattention criteria were met, and one or both of either disorganised thinking or altered levels of consciousness criteria were met.

5.2 Secondary outcomes

Severity and Subtypes

The 13 items from Delirium Rating Scale-Revised-98 contribute to a severity score (items are scored zero to three, range from zero [no delirium] to 39 [maximum severity]) including two items which also define hyperactive (score ≥ 1 on motor agitation), hypoactive (score ≥ 1 on motor retardation), mixed motor (score ≥ 1 on both motor items) or no motor (score=0 on both motor items) subtypes of delirium.

Visual analogue scale (VAS)

Pain scores are measured using VAS (ranges from 0 [no pain] to 100 [worst pain], assessed daily, over the seven days and the highest pain score will be reported as continuous data. The first three days' VAS also will be analysed by comparison between groups.

30-day mortality is all-cause mortality during 30 days post-surgery.

Length of hospital stay is calculated from the first post-operative day to discharge.

Costs of the anaesthetic procedure include the expenditure of anaesthesia; anaesthetic drug, and labour cost.

Total in-hospital costs include the expenditure of anaesthesia, surgery, and hospitalisation.

5.3 Subgroups:

Pre-delirium is defined as whether patients had delirium before the intervention, using the Confusion Assessment Method on the day of admission.

Pre-existing dementia is defined by the Mini-Mental State Examination (MMSE) score with thresholds adjusted for educational levels.

- MMSE scores from 0 to 17 without educational experience/illiteracy;
- MMSE scores from 18 to 20 with an educational level less than primary education;
- MMSE scores from 21 to 22 with an educational level less than high school diploma;
- MMSE scores from 23 to 24 with an educational level less than a bachelor's degree.

Age is categorised by groups 65 to 80 years vs >80 years.

6. Trial Population

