| 11. | Technical route:..... | 15 |
| 12. | Adverse event reports..... | 17 |
| 12.1 | Adverse events..... | 17 |
| 12.2 | Serious adverse events..... | 18 |
| 13. | Data management and statistical analysis..... | 20 |
| 14. | Test management..... | 22 |
| 15. | Test quality control..... | 19 |
| 16. | Data preservation..... | 20 |
| 17. | Publication of papers..... | 20 |
| 18. | References..... | 20 |

1. Background and significance of the study

Delirium, also known as acute consciousness disorder, is an acute organic brain syndrome with attention, feeling, thinking, memory, mental exercise, and sleep cycle disorders occurring in a short period, characterized by restlessness, multilingualism, orientation disorders, and unanswered questions. Age (≥ 65) and hip fractures are major risk factors for delirium. The incidence of delirium in elderly inpatients was reported in 14%~56%, while in elderly patients with hip fractures, the incidence of delirium was 32%~53.3% higher. An incidence of postoperative delirium was reported in 11.1%~44.8% in elderly patients. The incidence of postoperative delirium was higher in 20.3%~60.9% in elderly patients with hip fractures. After delirium occurs, diazepam or psychotic drugs are often needed to increase nursing requirements and the risk of falling while delaying the time of autonomous activity and hospital stay and increasing medical costs. During recovery, delirium increases mortality (figure 1), and disability can also increase the incidence of dementia. Dysfunction also causes persistent depression or anxiety.

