- 1) Is there any difference between general anesthesia and local anesthesia in the occurrence, severity, attack type, and delirium duration after hip fracture in the elderly? Which anesthetic method can reduce the incidence of postoperative delirium?
- 2) Is there a difference in the effect of the two anesthetic methods on postoperative delirium in different older people (elderly, dementia, or delirium)?
- 3) Do various factors (hypotension, drugs, pain, etc.) during anesthesia affect postoperative delirium and extent?
- 4) To analyze whether the control of anesthesia can reduce the medical expenses and related economic benefits caused by delirium.
- 5) The relationship between the classification and duration of delirium and patients' prognosis; does delirium lead to long-term cognitive dysfunction? How does it affect patients and their families' quality of life? The survival rate in patients with delirium?

2. Research topics

A randomized, controlled, multicenter, prospective study of the effect of local and general anesthesia on postoperative delirium in elderly patients with hip fractures

3. Purpose of the study

To evaluate the effect of two anesthetic methods on the incidence and prognosis of delirium in elderly hip fracture

4. Research Design

using prospective, multicenter, large sample, randomized controlled study design. Randomly enter local anesthesia group or general anesthesia group at 1:1.

According to the domestic literature report of postoperative delirium in elderly patients, the sample size estimation estimated that postoperative delirium incidence is about 26. Assuming that postoperative delirium incidence after local anesthesia is less than 30% of general anesthesia, the calculated sample size is 441 $n\alpha=$ each group. The provisional total sample size is 1000 cases. The sample size can be adjusted according to the progress of the study and the results in the medium term.

The number of cases in each center is 100. Because of the central random system, the number of cases in each center can be automatically adjusted according to the actual situation of the subjects recruited.

5. Case selection

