5.1 Research population

Elderly patients with acute (≤ 3 weeks) hip fractures on one side need surgical treatment.

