| Alanine aminotransferase | * | * | * | * | * | * | * | * |
| Album | * | * | * | * | * | * | * | * |
| Urea nitrogen | * | * | * | * | * | * | * | * |
| Creatinine | * | * | * | * | * | * | * | * |
| PH | * | * | * | * | * | * | * | * |
| PO2 | * | * | * | * | * | * | * | * |
| PCO2 | * | * | * | * | * | * | * | * |
| HCO3 | * | * | * | * | * | * | * | * |
| Na | * | * | * | * | * | * | * | * |
| K | * | * | * | * | * | * | * | * |
| Cl | * | * | * | * | * | * | * | * |
| Delirium CAM or not | * | * | * | * | * | * | * | * |
| DRS-R-98 of type and severity of delirium | * | * | * | * | * | * | * | * |
| VAS pain score | * | * | * | * | * | * | * | * |

Table 2: Other data to be collected

| Period | Data | Method |
|---------------------------|--|--|
| Preoperative general data | Age, sex, address, type of fracture History, ASA rating Cognitive function (MMES) | Medical records MMSE |
| Intraoperative | Methods of operation, level of the surgeon, manner of anesthesia Anesthesiologist level, anesthetic substance, and dosage Low blood pressure | Review of medical records and anesthesia records |

| | | |
|------------------------------|---|--|
| | Duration of operation estimated blood loss | |
| Postoperative | Length of stay, hospitalization costs, anesthesia costs, adverse events, mortality during hospitalization,30-day mortality, withdrawal from the study | Telephone follow-up |
| 6 months and 12 months later | Whether delirium occurs, type and severity Mortality Quality of life, anxiety or depression | Quality of life scale SF-36, anxiety and depression scale (HADS) Review of patients' families |

11. Adverse event reports

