6.2 Baseline Characteristics

Categorical data will be summarised by frequencies and percentages. Continuous data will be summarised by the number of responses, mean and standard deviation if deemed to be normally distributed, and the number of responses, median and interquartile range or total range if data appear skewed. Tests of statistical significance will not be undertaken, nor confidence intervals presented ⁷.

7. Statistical Analysis

7.1 Primary outcome:

The primary outcome is the incidence of postoperative delirium during 7 postoperative days, diagnosed with the Confusion Assessment Method, and will be a categorical variable.

7.2 Secondary outcome measures are as follows:

- The subtype, severity, and duration of delirium in 7 days after the surgery, diagnosed with the Delirium Rating Scale-Revised-98 and confusion Assessment Method, subtypes and duration of delirium are categorical variables, and severity score is a continuous variable;
- Duration of delirium, measured by days from the onset of delirium symptom to the resolution of symptoms, which is a continuous variable;
- The intensity of postoperative pain, measured with acute pain score in 7 days after the surgery using Visual Analogue Scale (VAS), which is a continuous variable;
- The occurrence of non-delirium in-hospital complications within 30 days after surgery, including chest infection, myocardial infarction, renal failure, gastrointestinal ileus, which is a categorical variable;
- Length of hospital stay, measured by the sum of inpatient days from admission to discharge, which is a continuous variable;
- Mortality during the hospital stay and during the follow-up period after hospital admission, which is a categorical variable;
- Incidence of delirium in the clinic or at the residence on 30-day, 6 months, 12 months after surgery, diagnosed with CAM, which is a categorical variable;
- Cognitive and functional decline on 30-day, 6 months, 12 months after surgery, diagnosed with Mini-Mental State Examination (MMSE) and Hospital Anxiety and Depression Scale, which is a categorical variable;
- Quality of life on 30 days, 6 months, 12 months after surgery, using 36-Item Short Form questionnaire, which is a categorical variable;

- Economic parameters, including total cost in hospital and expenditure for anesthesia and resource using costs, including equipment and disposables required for each anesthetic technique, which are the continuous variables.

8. Analysis Methods

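### The MMSE definition of pre-existing dementia ignores delirium at the time of testing, so the dementia interaction is partly a delirium interaction

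*SAP*

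**What the plan says.** SAP 5.3 gives the definition: "Pre-existing dementia is defined by the Mini-Mental State Examination (MMSE) score with thresholds adjusted for educational levels". Four education bands follow: 0 to 17, 18 to 20, 21 to 22 and 23 to 24. No prior diagnosis, informant report or CAM result is required.

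The score comes from the preoperative row of Table 2 in protocol section 10, which lists "Age, sex, address, type of fracture History, ASA rating Cognitive function (MMES" (a misprint for MMSE, as the method column shows). No day is given.

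Protocol 5.1 describes the population: "Elderly patients with acute (≤ 3 weeks) hip fractures on one side need surgical treatment". Delirium is not among the exclusions in 5.3. It is a second planned subgroup, which SAP 5.3 defines as follows: "Pre-delirium is defined as whether patients had delirium before the intervention, using the Confusion Assessment Method on the day of admission". The description under protocol section 9 instead counts preoperative delirium from admission up to surgery.

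Both subgroups enter SAP section 9 as separate interaction terms on the primary outcome. They serve SAP Aim 1 and protocol question 2, which asks about "postoperative delirium in different older people (elderly, dementia, or delirium" as different kinds of patient.

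SAP 7.2 also lists "Cognitive and functional decline on 30-day, 6 months, 12 months after surgery", based partly on the MMSE.

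**The concern.** Protocol section 1 describes delirium as an acute disturbance that includes attention, thinking and memory. A test of cognition taken during delirium can therefore score below the patient's usual level. The SAP definition treats that score as evidence of a pre-existing condition, and nothing in either document prevents testing during delirium or repeats the test once it clears.

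The two windows for preoperative delirium make this worse. A patient who becomes delirious after the day of admission, and is then given the MMSE, could be recorded as having dementia and no preoperative delirium.

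At stake is the answer to Aim 1. If acute delirium partly decides who is in the dementia subgroup, the interaction test cannot say whether dementia or delirium modifies the effect of anaesthesia. SAP section 9 looks at effects within subgroups only when the interaction has p < 0.05, so a distorted interaction also decides whether those effects are examined at all.

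**Working it through.** The plan gives no figure for dementia, preoperative delirium or MMSE error. Its one relevant calculation, the sample size, is not in dispute. With 26% v 18.2%, two-sided 5% and 80% power, the unpooled formula gives (1.960 + 0.842)² × (0.26×0.74 + 0.182×0.818) / 0.078² = 440.3, so 441 per group as stated. The dementia label does not enter it.

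**1. How the bands behave (hypothetical scores).** Take a patient in the 21 to 22 education band. A usual score of 26 lowered to 21 by delirium earns the dementia label. A usual score of 21 lowered to 15 falls below the band and, read literally, loses it. Delirium can move patients either way.

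**2. How many labels could be wrong.** Here the bands are read as upper cut-offs, every true dementia case is labelled, and delirium is independent of dementia. Assumed inputs:
- true dementia D = 15% or 30%;
- preoperative delirium L = 10%, 32% or 53.3%. The last two come from protocol section 1 ("in elderly patients with hip fractures, the incidence of delirium was 32%~53.3% higher"), whose wording is unclear and not confined to the time before surgery;
- share f of delirious patients without dementia who score in the dementia range = 25%, 50% or 75%.

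False labels = (1 − D) × L × f. True share = D / (D + false labels).

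| D | L | f | False labels per 1000 | True share |
|---|---|---|---|---|
| 30% | 10% | 25% | 17.5 | 94% |
| 30% | 32% | 50% | 112 | 73% |
| 15% | 32% | 50% | 136 | 52% |
| 15% | 53.3% | 75% | 340 | 31% |

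Suppose dementia itself modifies the effect, with RR 0.5 with and 0.9 without it and equal control risk. The true ratio of RRs is 0.5/0.9 = 0.56. The observed ratio is [true share × 0.5 + (1 − true share) × 0.9] / 0.9, which runs from 0.58 to 0.86 over these cases. The interaction shrinks.

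**3. If delirium, not dementia, modifies the effect.** All inputs are assumed. Per 1000 patients:
- 200 have dementia and 200 are delirious before surgery, 100 of them with dementia;
- 70% of the 100 delirious patients without dementia, and 5% of the 700 patients with neither, are labelled;
- postoperative delirium is 80% in both arms for every preoperatively delirious patient, and 35% (GA) v 24.5% (RA) for everyone else.

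*Correct labels.* With dementia (100 delirious, 100 not): RR = (80 + 24.5)/(80 + 35) = 0.909. Without (100 delirious, 700 not): (80 + 171.5)/(80 + 245) = 0.774. Ratio 1.17.

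*MMSE labels.* With (100 + 70 = 170 delirious, 100 + 35 = 135 not): (136 + 33.1)/(136 + 47.25) = 0.923. Without (30 delirious, 665 not): (24 + 162.9)/(24 + 232.75) = 0.728. Ratio 1.27.

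*CAM-negative patients only.* RR 0.245/0.35 = 0.70 in both groups. Ratio 1.00.

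For preoperative delirium of 10% and 30%, the dementia-group RR moves from 0.830 to 0.853 and from 0.962 to 0.963. The ratio moves from 1.12 to 1.20 and from 1.20 to 1.30. Dementia modifies nothing here, yet the all-patient comparison shows an interaction. Much of it remains with correct labels, because more of the patients with dementia are delirious. The CAM-negative restriction removes it.

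**4. Decline, only if it means a fall of at least 3 points from the preoperative MMSE.** Assume a true mean fall of 1 point, SD of change 3, and delirium gone by follow-up. The true rate is Φ((−2.5 + 1)/3) = 31%. If delirium lowered the baseline by 2 or 6 points, the rate seen in those patients is Φ(−3.5/3) = 12% or Φ(−7.5/3) = 1%.

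**The case against.** Several points on the other side are sound.

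- **Status.** SAP section 9 calls subgroup output exploratory, and the primary analysis is untouched. This stands and limits the consequence. It does not remove it: the comparison is Aim 1, and SAP 4.3 describes each comparison as hypothesis-driven.
- **No arm bias.** Allocation is 1:1, so errors should balance if MMSE testing does not depend on allocation. This stands, with one gap: randomisation is one day before surgery, and the documents do not say whether the MMSE comes first.
- **Other data exist.** Protocol Table 1 schedules CAM and DRS-R-98 before surgery, and protocol section 1 credits DRS-R-98 with separating delirium from Alzheimer's disease. This stands, but the dementia definition uses neither.
- **Overlap is not itself an error.** Each subgroup is tested separately, and the plan does not call them exclusive. This stands too; the fault lies in what the label measures.

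Stronger readings are tempting. A reader might infer that the plan codes delirium as dementia as a rule, wherever the cut-points lie. Three of the four bands have lower limits, so a very low score in a schooled patient falls in no band. A reader might also infer that mislabelling alone strongly distorts the RR in the dementia group. That result appears only if delirious patients without dementia are given a different treatment effect from delirious patients with it. Treated alike, the RR moves by 0.014 (0.909 to 0.923).

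**Conclusion.** The concern holds as a risk of unknown size. The definition, applied as written, can record an acute state as pre-existing dementia, or under the literal bands remove a patient from that group. The dementia interaction then partly reflects delirium. The direction depends on which condition modifies the effect: the interaction shrinks in step 2 and appears from nothing in step 3. Both steps rest on assumed inputs, because the documents give no preoperative delirium rate, dementia rate or MMSE error rate.

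The reach is one exploratory subgroup analysis and, conditionally, one secondary outcome. No bias between arms is shown, and the primary analysis and the 441 per group stand.

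A reader might infer that recovery from delirium will hide long-term cognitive decline. That needs decline to be change from the preoperative MMSE. SAP 7.2 calls the outcome categorical and names no reference score or cut-off, and SAP 8.2 has no model for it. The 6- and 12-month row of protocol Table 2 omits the MMSE, although protocol section 9 lists it as a follow-up outcome. Step 4 therefore shows what would follow from that choice, not what the plan does.

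**What to change.** 1. In SAP 5.3, apply the MMSE dementia label only to patients who are CAM-negative at the preoperative assessments. Alternatively, keep all patients and rename the subgroup 'low preoperative MMSE'.
2. Reconcile the admission-day window for preoperative delirium in SAP 5.3 with the admission-to-surgery window in protocol section 9. Until this is done, CAM-negative has no single meaning, and a patient delirious at the MMSE could still pass.
3. In SAP section 9, report the dementia interaction in preoperatively CAM-negative patients alongside the all-patient version.
4. State whether the bands are upper cut-offs or closed ranges.
5. State how cognitive decline is defined. If it is change from the preoperative MMSE, use the change score only in patients CAM-negative before surgery, and report follow-up MMSE without change for the others.

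Dementia status should not be taken from the history item in Table 2 unless it is confirmed that dementia diagnoses are recorded there; the table does not say so.

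The changes are mainly SAP wording, because preoperative CAM and MMSE are already scheduled. The price is a smaller dementia subgroup and a less precise interaction estimate. The sample size does not change.

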8.2 Secondary outcomes (SO)

SO1: Frequency counts will be summarised by treatment group. RR and associated 95% CI will be calculated.

SO2: Duration of delirium will be summarised using basic descriptive statistics and analysed using generalised linear model (GLM) methods.

SO3: Acute pain score using VAS will be summarised using basic descriptive statistics and analysed using GLM methods.

SO4: Occurrence of non-delirium in-hospital complications within 30 days after surgery will be summarised by treatment group, but no relative effect will be calculated.

SO5: Length of hospital stay will be summarised using median and IQR and analysed using GLM methods.

9. Planned subgroup analyses

Interpretation of subgroup analysis will be treated with caution (output will be treated as exploratory rather than definitive⁸). Analysis will be limited to the primary outcome, which is the incidence of postoperative delirium during 7 postoperative days, and the following subgroups

- Age, as defined by 65-80, >80
- Preoperative dementia, those with vs those without
- Preoperative delirium, those with vs those without.

The effects of these subgroups will be examined by adding the subgroup by treatment group interaction parameters to the log-binomial model. Wald tests will determine statistical significance (p-values) of these interaction parameters. Differences between the treatment groups within subgroups will only be examined if the interaction parameter is shown to statistically important (p-value <0.05).

10. Definitions and Derived Variables

Abbreviations & Definitions	
Abbreviation/acronym	Meaning
BCTU	Birmingham Clinical Trials Unit
BP	Blood Pressure
CONSORT	Consolidated Standards of Reporting Trials
DMC	Data Monitoring
ITT	Intention to Treat
SAE	Serious Adverse Event
SAP	Statistical Analysis Plan
TSC	Trial Steering
POD	Postoperative Delirium
GA	General Anesthesia
RA	Regional Anesthesia
GLM	Generalised Linear Model
Term	Definition
International Standard Randomized Controlled Trial	A Clinical Trial Registry
Protocol	Document s details the rationale, objectives, design, methodology, and statistical considerations of the study
Randomisation	The process of assigning trial subjects to Intervention or control groups using an element of chance to determine the assignments in order to reduce bias.
Statistical Analysis Plan	Pre-specified statistical methodology documented for the trial, either at the protocol or in a separate document.

11. Software Details

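### SAP 5.3 defines dementia by closed MMSE bands, so coded as written the lowest-scoring schooled patients fall into the group without dementia

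*SAP*

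**What the plan says.** The subgroup definitions in SAP 5.3 base pre-existing dementia on the MMSE and promise "thresholds adjusted for educational levels". Four rows follow. The first, for unschooled patients, starts at zero: "MMSE scores from 0 to 17 without educational experience/illiteracy". The second does not; its lower limit is one point above the top of the first: "MMSE scores from 18 to 20 with an educational level less than primary education". The third and fourth continue the pattern, with bands of 21–22 for schooling short of high school and 23–24 for schooling short of a university degree.

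SAP section 9 then lists the subgroup as "Preoperative dementia, those with vs those without" and tests it by adding a treatment-by-subgroup interaction to the log-binomial model, with a Wald test. It also sets a gate: "Differences between the treatment groups within subgroups will only be examined if the interaction parameter is shown to statistically important (p-value <0.05". The same section says of the subgroup results that "output will be treated as exploratory rather than definitive". Existing cognitive impairment is one of the three factors named in Aim 1 of SAP 2.2.

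**The concern.** The lead-in speaks of thresholds, but the rows are closed intervals. A threshold makes everyone at or below it a case. A closed interval makes only those inside it a case, and section 9 leaves *without* as the only place for the rest. The coded variable then does not follow impairment. With schooling below high school, a score of 22 is *with* dementia and a score of 5 is *without*.

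If the treatment effect differs by true impairment, mixing the most impaired schooled patients into *without* pulls the two subgroup estimates together. The p<0.05 gate may then withhold results that would otherwise have been examined. Any subgroup table would also carry a misleading row label.

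**Working it through.** **Plan's own figure.** The documents give no number for the dementia factor. The only design figure is the 441 per group in SAP 3.3. With 26% against 0.70 × 26% = 18.2%, two-sided 5% and 80% power, the unpooled formula gives (1.960 + 0.842)² × (0.26×0.74 + 0.182×0.818) / 0.078² = 440.3, so 441. It is reproduced, and the point does not depend on it.

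**Enumeration of the rule.** All MMSE scores from 0 to 30 were run through the four rows under three readings: closed bands with exclusive classes, closed bands with nested classes (less than primary is also less than high school, and so on), and upper cut-offs only.

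| Education row | Closed, exclusive | Closed, nested | Upper cut-off | Low scores lost |
|---|---|---|---|---|
| None | 0–17 | 0–24 | 0–17 | none |
| Less than primary | 18–20 | 18–24 | 0–20 | 0–17 (18 values) |
| Less than high school | 21–22 | 21–24 | 0–22 | 0–20 (21 values) |
| Less than bachelor's | 23–24 | 23–24 | 0–24 | 0–22 (23 values) |
| Bachelor's or above | no row | no row | no row | all 31 values unmatched |

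Lost values in the three schooled rows: 18 + 21 + 23 = 62. Values at or below their upper limits: 21 + 23 + 25 = 69. The 62 are the same under both closed readings. Nesting adds a second error: 7 + 4 + 2 = 13 values above a class's own limit become *with* (unschooled 18–24, less than primary 21–24, less than high school 23–24). These are counts of score values, not of patients.

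**How precise the interaction test is.** At 441 per arm the variance of the overall log RR is 0.74/(441×0.26) + 0.818/(441×0.182) = 0.0166, so the SE is 0.129. Suppose, as a simplification, the same risks in both strata and a share s of patients with dementia. The interaction SE is then 0.129/√(s(1−s)): 0.258 at s = 0.5, the most favourable split, and 0.282 at s = 0.3. For 80% power the ratio of the two RRs must be at least exp(2.80 × 0.258) = 2.06, or exp(2.80 × 0.282) = 2.20. The test is weak even with correct coding.

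**Illustration of dilution, on assumed inputs.** The documents give no education mix, MMSE distribution or prevalence of impairment. Assume exclusive classes, no graduates, MMSE SD 5, and a mean 2 to 3 points above each upper limit. Then 31–38% of patients are at or below their limit (π), and 44–63% of the impaired schooled patients lie below their band. If half of the impaired are unschooled, the miscoded share of all impaired is m = 0.22–0.32. Further assume a GA risk of 0.40 in the impaired, a true *without* RR of 0.60, and the SAP's overall 26% and RR 0.70.

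- For π = 0.31: g₀ = (0.26 − 0.31×0.40)/0.69 = 0.197, and the impaired RR is r₁ = (0.182 − 0.69×0.197×0.60)/(0.31×0.40) = 0.81.
- At m = 0.22, the observed *without* RR is (0.31×0.22×0.40×0.81 + 0.69×0.197×0.60)/(0.31×0.22×0.40 + 0.69×0.197) = 0.635.
- Shrinkage of the log interaction is 1 − ln(0.81/0.635)/ln(0.81/0.60) = 19%.
- Over the whole range, shrinkage is 19–34%, and Wald power falls from 16–22% to 10–16%, a loss of 4–8 percentage points.
- With a *without* RR of 0.65 instead, power is 8–9% under correct coding and the loss is 1–2 points.
- With a common RR of 0.70 the interaction is zero under either coding, and the rejection rate stays at 5%.

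**The case against.** The strongest reply is that the intent is plain. The lead-in says thresholds, and the bands run on without gaps, as in a stepped table of cut-offs. Few analysts would code a schooled patient scoring 10 as free of dementia. That is a fair account of what was meant, and it supports the remedy. It does not cure the rule: nothing elsewhere in the SAP or protocol restates it. An analyst who infers upper cut-offs must still decide how to separate overlapping education classes and what to do with graduates.

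A second reply is that the stakes are small: the analysis is exploratory, is confined to one outcome, and would seldom pass the gate even if coded correctly. This stands. The loss of power above depends wholly on assumed inputs and nearly vanishes under a modest change in one of them.

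A third reply is that section 9 does not say what to do with a patient who matches no row. They might be left unclassified rather than called *without*. They would then drop out of the interaction model, and the most impaired schooled patients would still be missing from *with*.

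**Conclusion.** The rule in SAP 5.3 is wrong as written. Under either reading of the education classes, 62 of the 69 low score values in the three schooled classes meet no dementia criterion, and graduates have no rule at all. That conclusion rests on the text alone. The consequence is a wrongly built variable for one exploratory subgroup analysis. Its effect on the estimate cannot be computed from the documents.

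A reader might infer more, and the documents do not support it:

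- That the data were in fact miscoded. No document shows how the variable was derived.
- That the primary result or type I error is at risk. The primary analysis does not use the variable. The MMSE is listed among preoperative data in protocol Table 2, so even a miscoded baseline factor leaves the randomised comparison intact.
- That much power is lost. There was little to lose.
- That education was not collected. Its absence from the summary in Table 2 does not show that.
- That the preoperative delirium subgroup is wrongly defined. SAP 5.3 asks about delirium preceding the intervention but takes the CAM from the admission day, while the description under protocol section 9 counts delirium up to surgery. The protocol sentence concerns incidence, not a subgroup factor, and an admission-day CAM would ordinarily precede randomisation, which SAP 3.2 places one day before surgery. This is a wording mismatch to reconcile, no more.

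**What to change.** In SAP 5.3, before unblinding:

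1. Replace the closed bands by upper cut-offs at the bands' own limits: ≤17, ≤20, ≤22 and ≤24.
2. Define the education classes so that each patient belongs to exactly one.
3. Have the sponsor state the rule for a bachelor's degree or above.
4. Confirm that education level is recorded, and say how a patient with missing MMSE or education is handled.

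As a separate tidy-up, reconcile the admission-day CAM with the protocol's admission-to-surgery wording. Protocol Table 1 schedules a single preoperative CAM without fixing its day, so a later preoperative assessment should not be presumed to exist.

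The cost is a few lines of text. No new data are needed if education is on the case report form, and the sample size and primary analysis do not change.
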